- Ventilator collected parameters during the EFL screening and titration; delta Xrs value, % flow limited breaths, EPAP values and mask leak values.

VII. Assessment of Safety

All serious adverse events occurring during the course of the study and up to 72 hours post study visit will be collected, fully documented, and reported to Western Institutional

Determination of the Prevalence and Severity of Expiratory Flow Limitation in Chronic Obstructive Pulmonary Disease Patients

Review Board by the Principal Investigator, [name], MD or sponsor staff per IRB guidelines. Serious adverse events will be reviewed by the Sponsor within 24 hours of the study team being aware of the event.

A serious adverse event (SAE) is an adverse event:

- Resulting in death, or
- Resulting in a serious deterioration in the health of the subject that:
 - Results in a life-threatening illness or injury,
 - Results in a permanent impairment of a body structure or body function,
 - Requires inpatient hospitalization or prolongation of existing hospitalization, or
 - Results in medical or surgical intervention to prevent permanent impairment of a body structure or body function.

All unexpected adverse events during the course of the study and up to 72 hours post study visit will be collected and reviewed. As any events will be reported electronically or directly from a person, the study team will collect the onset, duration, intensity and treatment required, outcome and action taken. In addition to adverse event reporting, the study staff will report a summary of the protocol findings, participant recruitment, drop-outs, and events to the IRB annually.

VIII. Device Deficiencies

All device deficiencies, use or user errors, and equipment failures will be documented.

Use or User errors will be captured as part of the source documentation. Device deficiencies and equipment failures will be kept on a separate log. The serial numbers and type of deficiency/failure will be captured. Unanticipated device deficiencies that lead to SAE's will be reviewed with the PI and reported to the IRB as required.

IX. Statistical Methods

Determination of Sample Size

Approximately 100 participants will be enrolled. No power analysis was performed.

General Considerations

Descriptive statistics will be presented for all variables of interest. Continuous data will be summarized by mean, standard deviation, median, minimum, and maximum values.

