Categorical data will be presented as frequencies and percentages. Any formal significance testing will be performed at $p < 0.05$.

There are no statistical criteria for terminating the study, and any deviations to the original statistical plan will be noted in the analysis report.

Determination of the Prevalence and Severity of Expiratory Flow Limitation in Chronic Obstructive Pulmonary Disease Patients

Primary Analysis

The primary analysis will calculate the prevalence of EFL, including the 95% Binomial confidence interval (CI).

Secondary Analysis

Correlations between device parameters and efficacy outcomes will be performed using Pearson and Spearman correlation. Percentage of participants exhibiting EFL abolition with Vector therapy will be presented, including the 95% Binomial confidence interval (CI).

Exploratory Analysis

Various exploratory analyses may be performed to help evaluate participant's therapy settings with other baseline data or outcomes, but these analyses are not required for the final report

Participant Disposition

Participant disposition, including the total number of participants enrolled, completed, early terminations and withdrawals, will be presented. A listing will be provided with the reasons for discontinuation.

Safety Analysis

Safety evaluations will be performed by recording clinical adverse events at the time originally reported, and they will be followed at regular intervals until resolution or study completion, whichever comes first. Adverse events will be provided in data listings.

Interim Analysis

An interim analysis may be performed after approximately 50% of the planned study population has completed the study.

X. Direct Access to Source Data / Documents

Only site clinical study staff will know the identity of the participants. All information recorded by the study team and provided for analysis will be given a study ID number.

Privacy rules and requirements according to federal and state governing regulations will be implemented. All the information collected as part of this study will be kept confidential. All information collected for this study will be kept in a secured area or stored in a password protected computer if digital. Except when required by law, participants will not be identified by name, social security number, address, telephone number, or any other direct personal identifier in study records. For records disclosed to Philips participants will be assigned a unique code number.

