The PI and study personnel will be trained to the study protocol, study product, TMF documents, monitoring plan, CRFs and/or eCRFs, direct data reporting, and all Sponsor expectations, as applicable. Once complete, training and delegations will be documented for PI and study personnel.

Data queries will be addressed by delegated study personnel and CRF/ eCRFs will be reviewed and signed off by PI prior to study closure. Monitoring will be completed in accordance with US CFR, ICH-E6 GCP Section 6, and ISO 14155:2011 as applicable.

XII. Ethics

This study will be submitted and reviewed by the Western Institutional Review Board. All participants will be consented prior to completing the trial. The Principal Investigator will review all adverse events as it relates to the study device.

All data will be kept confidential and in a secure location if on paper or on a secure server or device. Only approved study personnel will have access to study related documents. All electronic data shall be stored in a coded data set. All paper documents shall be kept in a secure area. Study data and source will be made available for study related monitoring or audits by the IRB/IEC, sponsor, or regulatory inspection(s). Results of the study related data, and information obtained from the engineering study, will be collected, received and reported by Philips. Philips will use participant study data for research purposes to support scientific and marketing objectives described in this protocol.

XIII. Data Handling and Recordkeeping

Hard copies of the study will be kept on site for at least 2 years after study completion. The sponsor will maintain study records indefinitely. Records will be stored at Iron Mountain, a secure information management services company.

XIV. Financing and Insurance

If the participant is injured during the course of the trial and as a direct result of this trial, they should contact the Principal Investigator, [name]. The participant will be directed to seek clinically appropriate medical care for that injury. However, we cannot guarantee that the medical care and treatment will be provided without charge or that it will be paid for by the participants insurance company, and the costs incurred may ultimately be the participant's responsibility.

XV. Registration on ClinicalTrials.gov or other applicable registry

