This trial will be registered on Clinical Trials.gov. It is the intent that these data may be used for to support regulatory clearance and/or consideration for a submission to peer review publication.

XVI. Risk and Benefit Analysis

A. Potential Risks and Discomforts

This is a minimal risk study. Potential risks are detailed below and will be listed in the ICF and discussed during the consenting process.

We believe that the risks of providing noninvasive ventilation with the Vector NIV device are no greater than the risks encountered with other assisted positive airway pressure (PAP) devices. We believe that no significant risks will be posed to the participants participating in this protocol, as the study is noninvasive and will be conducted in a clinical

Determination of the Prevalence and Severity of Expiratory Flow Limitation in Chronic Obstructive Pulmonary Disease Patients

supervised setting by trained clinical staff. The equipment has been tested to ensure safety. Should the equipment not perform as designed, therapy could increase and / or decrease more than desired. This affect could be uncomfortable.

A trained study staff member will be present monitoring the participant while the device is in use at the clinic. The study staff member will intervene should any problems be identified. One possible intervention could be for the staff to stop the study in the event that participant's oxygen saturation (SpO_2) falls below 88%. The participant can also easily remove their interface device should it become uncomfortable or make breathing difficult. Other potential side effects of PAP therapy may include: ear discomfort, conjunctivitis, skin abrasions due to non-invasive interfaces and gastric distension (aerophagia), all of which are quite uncommon. Thus, we believe that the risks and discomfort are minimal.

COVID-19 is a risk with any in-person activity, but proper mitigation strategies, including COVID-19 screening, disinfection, and other site safety procedures, will be implemented to minimize patient risk.

We believe that the risks and discomforts associated with this study are minimal.

B. Potential Benefits

Although participation in this trial will not result in any direct benefit to the subjects, they will be contributing to generalizable data that will help provide the sponsor and investigator more insight into the prevalence of expiratory flow limitation in the COPD patient population.

C. Compensation for Research-Related Activities

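### Section VII limits collection of non-serious adverse events to undefined unexpected ones, while sections IX and XII set no such limit, so the safety listing could miss expected minor device effects

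*Combined protocol and SAP*

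**What the plan says.** Section VII (Assessment of Safety) names two classes of event for collection, each during the study and to 72 hours after the visit. The first is serious adverse events, which it defines. The second is set by this sentence: "All unexpected adverse events during the course of the study and up to 72 hours post study visit will be collected and reviewed". Neither section VII nor the glossary says what makes an event unexpected.

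The same section goes on: "As any events will be reported electronically or directly from a person, the study team will collect the onset, duration, intensity and treatment required". It also says that "the study staff will report a summary of the protocol findings, participant recruitment, drop-outs, and events to the IRB annually".

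Section IX (Safety Analysis) is worded without the restriction: "Safety evaluations will be performed by recording clinical adverse events at the time originally reported", and "Adverse events will be provided in data listings". Section XII (Ethics) states: "The Principal Investigator will review all adverse events as it relates to the study device".

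Section XVI.A (Potential Risks and Discomforts) names the foreseeable minor effects: "Other potential side effects of PAP therapy may include: ear discomfort, conjunctivitis, skin abrasions due to non-invasive interfaces and gastric distension". It describes them as "all of which are quite uncommon" and says that the potential risks will be listed in the consent form.

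**The concern.** The rule that tells the site what to collect carries a limiting word, and the section that tells the statistician what to list does not. A listing can show only what the site recorded. If staff follow section VII to the letter, a non-serious effect already named in section XVI need not be collected. The section IX listing would then be short of events that its own wording appears to cover, and nothing in it would reveal the gap.

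What is at stake is the completeness of the safety listing. That matters somewhat here because section I describes the Vector ventilator as investigational and section XV says the data may be used in support of regulatory clearance. Section XVI.A also states a belief that the device's risks do not exceed those of other positive airway pressure devices. The familiar effects of such devices bear directly on that belief, and they are the ones section VII does not clearly require.

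**Working it through.** No arithmetic applies: the documents give no adverse event rate, and none is assumed. The check sets the relevant text side by side.

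| Place | What it governs | Limit by seriousness or expectedness | Window |
|---|---|---|---|
| VII, first rule | Collection, documentation, reporting | Serious only (defined) | To 72 hours after the visit |
| VII, second rule | Collection and review | Unexpected only (not defined) | To 72 hours after the visit |
| VII, following sentence | Reporting route and details recorded | None stated | None stated |
| VII, yearly summary | Report to the IRB | None stated | Annual |
| IX, Safety Analysis | Recording, follow-up, listing | None stated | Recorded when reported; followed to resolution or study completion |
| XII, Ethics | Investigator review | None stated; tied to the study device | None stated |

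Now trace one example, a non-serious skin abrasion from the mask.

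1. *Is it serious?* No, by the definition in section VII. The first rule does not reach it.
2. *Is it unexpected?* The term is undefined. On the ordinary meaning, an effect named in the protocol's risk section, and due to be named in the consent form, is expected. The second rule then does not require it.
3. *Does the following sentence of section VII bring it in?* Possibly. It speaks of any events, but it comes directly after the restricted rule and describes how reports arrive and which details are taken. It does not say that expected events are collected.
4. *Does section IX bring it in?* Read alone, yes: the abrasion would be recorded and listed. But section IX sets no period after the visit for which events are sought.
5. *Does section XII bring it in?* It would have to be reviewed. Review presupposes that someone has recorded it.
6. *Do the questionnaires catch it?* Section II lists a comfort assessment by questionnaire, and section III has a questionnaire completed after Vector use. Either might bring discomfort to light, but neither is stated to feed the adverse event records.

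Whether the abrasion reaches the listing therefore depends on which section the staff treat as governing. The same reasoning applies to ear discomfort, conjunctivitis and gastric distension.

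**The case against.** The strongest reply is that the rest of the protocol already covers these effects. Section IX is itself an instruction to record adverse events, with no limit by type. Section XII has all of them reviewed in relation to the device, which fits mask and pressure effects well. The sentence after the restricted rule in section VII speaks of any events. Section IV.C counts nausea and rash as adverse events, so minor events are plainly within the concept. Section X mentions side effects, in a garbled sentence, among the reasons for which records may be reviewed. A trained staff member is present while the device is in use (section XVI.A), and the sponsor's monitoring is meant to verify completeness (section V.B). Only listings are planned, with no adverse event rates or comparisons.

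Much of this stands. Section VII is the only place that sets the 72-hour window, but it is not the only place that bears on which events are recorded. A reader might infer that the protocol excludes expected effects, or that its sections flatly contradict one another. The documents do not support either: no passage excludes these effects, and sections IX and XII can be read as including them.

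Two things are left unanswered. None of the broader passages says that expected, non-serious events are collected up to 72 hours after the visit. And monitoring, which under section V.B also checks compliance with the approved protocol, would not necessarily flag an omission that a literal reading of section VII permits.

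**Conclusion.** The point holds as a minor one. The scope of collection in section VII is narrower on its face than the scope of recording and listing in section IX and of review in section XII, and the word that makes the difference is undefined. Staff who apply section VII literally could omit the expected, non-serious effects named in section XVI, and the listing could then be incomplete.

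The size cannot be put as a number. The protocol calls the effects uncommon, so few entries are likely to be at stake.

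The conclusion rests on two assumptions: that an effect named in the risk section would be treated as expected, and that no other study document widens the rule. The second cannot be checked, because the adverse event form and the monitoring plan are not in the documents, and either may already call for all events. For that reason a reader should not infer that expected effects will in fact go unrecorded, only that the protocol as worded allows it. Nor should a reader infer any damage to the main results: the primary and secondary estimates do not use adverse event data and are unaffected.

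**What to change.** In section VII, replace the opening words *All unexpected adverse events* with *All adverse events, expected or unexpected*, and keep the 72-hour window. Sections VII, IX and XII then agree on scope, and the undefined term no longer decides what is collected. Check that the adverse event form and the monitoring plan use the same scope.

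The cost is one phrase in the protocol and a few more minor events to log. If the sponsor already intends to collect everything, the edit only makes that explicit.

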- between 2.8 and 3.8 cm H₂O/l/s, inclusive, have indeterminate EFL. Some breaths were calculated to be flow limited.
- greater than 3.8 cm H₂O/l/s have EFL.

For purposes of this trial, participants who have indeterminate EFL or EFL (i.e., $\Delta\bar{X}_{rs}$ value is greater than or equal to 2.8 cm H₂O/l/s) will continue to titration.

This technology has been evaluated in numerous clinical studies for both the detection, reduction and abolishment of expiratory flow limitation in patients with COPD. In 1956, Dubios et al., demonstrated the FOT method to be applicable to the measurement of airway resistance in patients, evaluation of therapeutic procedures designed to relieve airway obstruction, separation of airway resistance from tissue resistance, and study of the multiple factors that may affect airway resistance.¹ And in additional work 2006, Dellaca et al., suggested the forced oscillation technique may be useful in chronic obstructive pulmonary disease patients using nasal pressure support by identifying continuous positive

Determination of the Prevalence and Severity of Expiratory Flow Limitation in Chronic Obstructive Pulmonary Disease Patients

airway pressure levels that support breathing without increasing lung volume, which in turn increase the work of breathing and reduce muscle effectiveness and efficiency.⁶

The Vector project has incorporated this method as a new feature into the Philips BiPAP Ventilator (Murrysville, PA) overall platform (K121623). The device has been designed to produce a 5 Hz sine wave with peak-to-peak amplitude of approximately 2 cmH₂O superimposed upon the pressure and flow generated by the device. The resultant feedback waveform is then filtered and analyzed to measure reactance (delta X_{rs}) and thus determine if EFL is present. Subsequently, the EPAP (and concurrently and proportionally the IPAP) is increased until the EFL is essentially abolished (falls below the predetermined EFL threshold). Since this reactance is analyzed continuously (breath by breath) during both inspiration and expiration, it is relatively immune to external factors such as modest leaks or coughing / swallowing.

Description of the Intervention Studied

Study Device Descriptions:

1. Vector Device

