The Resmon Pro (St. Paul, MN) also uses the forced oscillation technique (FOT) which is a noninvasive method to measure the mechanical properties of the lung and airways during tidal breathing. In addition to measuring total impedance (resistance and reactance), the Resmon Pro can measure expiratory flow limitation which is a key index of respiratory obstruction. Restech has developed patented technology to determine the breath-by-breath presence and severity of expiratory flow limitation (EFL) during quiet breathing. Using the Resmon Pro, a physician can detect the presence, severity and reversibility of EFL, and evaluate the degree of airflow obstruction and shortness-of-breath experienced by the patient.

The Resmon PRO FULL (K152585) is intended to measure respiratory system impedance using the Forced Oscillation Technique (FOT). Is intended for use with pediatric and adult patients 4 years of age or older. The device is designed to be used by pulmonologists, general practitioners, nurses, respiratory therapists, laboratory technologists, medical researchers and similarly trained personnel in hospitals, clinics, and private physician offices.

Resmon PRO FULL consists of a main unit which has been designed to be used stand-alone, without the need of any personal computer, and an adjustable holder with a clamp to fix such unit to a table/desk and to regulate its height and orientation to the patient during an FOT test.

II. Study Objectives and Purpose

Primary Objective

To gain insight and understanding on the prevalence and severity of expiratory flow limitation and how it relates to other physiological characteristics and endpoints in patients with COPD. For purposes of this trial, overall prevalence includes indeterminate EFL and EFL.

Secondary Objectives: To understand the correlation of the final EPAP with FEV1, final EPAP with screening delta Xrs value and the percent of participants with EFL per the Resmon Pro that have their EFL abolished during the Vector screening.

Primary Endpoint:

- Overall Prevalence of EFL, as defined as the percentage of participants exhibiting a Delta Xrs value greater than or equal to 2.8

Secondary Endpoint:

- Correlation of titrated Final EPAP to participants' FEV1
- Correlation of titrated Final EPAP to participants' screening Delta Xrs value
- Percent of participants with EFL per the Resmon Pro that have their EFL abolished during the Vector screening

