Exploratory Endpoints: – Correlation and relationship of participant's therapy settings to the following:

- Classification of COPD (Chronic Bronchitis or Emphysema)
- Airflow limitation severity in COPD via Global Initiative for Chronic Obstructive Lung Disease (GOLD) classification¹²
- Presence of indeterminate EFL and EFL in a seated position
- Presence of indeterminate EFL and EFL in a supine position
- Quality of Life via COPD Assessment Test (CAT)¹³ score
- Exacerbation History
- Healthcare Utilization
- Smoking History
- Oxygen therapy usage
- Documented PaCO₂
- Presence of Sleep Disordered Breathing and risk of obstructive sleep apnea (OSA) via STOP-BANG Questionnaire¹⁴
- Therapy Comfort assessment via Questionnaires

Determination of the Prevalence and Severity of Expiratory Flow Limitation in Chronic Obstructive Pulmonary Disease Patients

Device Related Exploratory Endpoints:

- Vector Device collected parameters: Delta Xrs value, % flow limited breaths, Total System Resistance mask leak values
- Comparison of Delta Rx calculation of the Resmon Pro at 5 Hz vs. Vector study ventilator
- Correlation between screening Delta Xrs (measurement in liters per second) at final EPAP in cmH₂O in supine position and any other variables from the analysis
- Therapy Comfort assessment via Questionnaires

Observational Endpoints/Learnings:

- Clinicians will be able to know when EFL is present or not present through the screening feature of the Vector device
- Understanding of how patients who present with varying degrees of EFL severity are being medically managed differently or similarly
- Percentage of patients that were successfully screened as not having EFL by the Vector device but determined to have flow limitation measured by Resmon Pro

III. Study Design:

This will be a cross-sectional, non-randomized epidemiology study designed to assess the prevalence and severity of expiratory flow limitation in a community COPD population. In the study we will also investigate how the presence of EFL may correlate to other physiological biomarker endpoints in the COPD patient.

Site COVID-19 safety procedures and documentation will be followed. Study devices and materials will either be single use or will be cleaned and disinfected per the Instructions for Use.

Schedule of Events:

Study Visit

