- EFL Determination: The participant will be asked to breathe quietly into the Vector device using the selected mask for 5 minutes in the seated position, and then an additional 5 minutes while in the supine or semi-recumbent position. This device has the capability of detecting EFL. If it is determined that the participant does not have EFL or indeterminate EFL by the device screening indicator, the participant will not continue with the EPAP titration.
- EPAP Titration: if it is determined by the Vector NIV device that the participant has indeterminate EFL or EFL (ΔX_{rs} value is greater than or equal to 2.8 cm H₂O/l/s)

Determination of the Prevalence and Severity of Expiratory Flow Limitation in Chronic Obstructive Pulmonary Disease Patients

the Vector NIV device will be changed from screening mode to therapy mode to delivery BiPAP therapy with the following settings.

Vector Device Settings:

• Pressure Support	6 cmH ₂ O
• Max Pressure	26 cmH ₂ O
• EPAP Min / EPAP Max	4 / 20 cmH ₂ O

- The participants will then breathe on the Vector NIV device in the supine position (preferred) or semi-recumbent if needed for approximately an additional 20 minutes. During the additional 20 minutes of breathing, the device will automatically increase the EPAP (and concurrently and proportionally the IPAP) until the EFL is abolished (or falls below the predetermined EFL threshold).
- While the automatic EPAP Titration is being performed, all participants' SpO₂ will be monitored via finger pulse oximetry.
- Patient must stay awake during the EPAP Titration. If the patient falls asleep, they will be woken by study staff.
- The Final EPAP that is determined to abolish the participants' EFL will be recorded. This value may be assessed by a Philips staff member using a software program designed to determine this value.
- Participants will complete an EFL Vector device post questionnaire

Unscheduled Visits:

This is a single visit study. There are no anticipated unscheduled visits.

IV. Selection and Withdrawal of Subjects:***A. Inclusion Criteria***

1. Age \geq 40 years of age; \leq 80 years of age
2. Ability to provide consent
3. Diagnosis of COPD

B. Exclusion Criteria:

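### The single EFL abolition percentage does not separate participants already below threshold at minimum EPAP from those whose EFL fell only after EPAP was raised

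*Combined protocol and SAP*

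**What the plan says.** Section IX, Secondary Analysis, gives the abolition endpoint one sentence: "Percentage of participants exhibiting EFL abolition with Vector therapy will be presented", with a 95% binomial confidence interval. It sets no comparator, success criterion or test.

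The path to that percentage is in Section III (EFL Determination, EPAP Titration, Vector Device Settings) and Section I:

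- **Entry.** A participant goes on to titration "if it is determined by the Vector NIV device that the participant has indeterminate EFL or EFL", that is, with a Delta Xrs of 2.8 cmH2O/l/s or more. Section I calls values from 2.8 to 3.8 indeterminate EFL and remarks of that band: "Some breaths were calculated to be flow limited".
- **Screening pressure.** The device description in Section I gives a fixed pressure, typically 3-4 cmH2O. Screening lasts 5 minutes seated and then 5 minutes supine or semi-recumbent.
- **Therapy settings.** "EPAP Min / EPAP Max" is 4 / 20 cmH2O, with pressure support of 6 cmH2O.
- **End of titration.** Over about 20 minutes the device raises EPAP "until the EFL is abolished (or falls below the predetermined EFL threshold". The threshold has no number here, and no number of breaths or time below it is given.

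Section II words the endpoint differently: "percent of participants with EFL per the Resmon Pro that have their EFL abolished during the Vector screening". That names another device for the denominator and another phase for the outcome.

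**The concern.** Participants are selected because a reading lay on one side of a cut-off, and the outcome is a later reading on the other side. Some will cross back without any effect of raising EPAP, most easily those in the indeterminate band. Because the EPAP floor coincides with the top of the screening range, a participant can be below threshold before EPAP has risen at all.

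Nothing in Section IX keeps such a participant apart from one whose EFL fell only after EPAP went up. The protocol describes raising EPAP as the means by which the device abolishes EFL, so a reader will take the percentage as the yield of titration. Section XV says the data may support regulatory clearance, and Section XII mentions marketing objectives. The figure may therefore be used as evidence about the device.

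The same participants would probably sit at or near the minimum Final EPAP in the two planned correlations.

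**Working it through.** **The plan's own figure.** There is none to reproduce. Section IX states that no power analysis was done, and no expected abolition rate or repeatability figure appears anywhere.

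**Inputs from the documents.** Entry cut-off 2.8; upper edge of the indeterminate band 3.8; screening pressure 3-4; EPAP floor 4; pressure support 6; about 100 participants. At the floor, IPAP is 4 + 6 = 10 cmH2O, so only the expiratory pressure matches screening.

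**Assumptions (not in the documents).** True Delta Xrs, T, is lognormal with median m = 2.0, 2.8 or 3.5 and log SD 0.7. Two readings are X1 = T + e1 and X2 = T + e2, with independent normal errors of SD s = 0.3, 0.5 or 1.0. There is no treatment effect and no change of pressure. The share truly at or above 2.8 is 1 − Φ(ln(2.8/m)/0.7):

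- m = 2.0: 1 − Φ(0.481) = 31.5%
- m = 2.8: 1 − Φ(0) = 50.0%
- m = 3.5: 1 − Φ(−0.319) = 62.5%

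**Step 1: everyone screened at 2.8 or above.** P(X2 < 2.8 | X1 ≥ 2.8), by simulation:

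| s | m = 2.0 | m = 2.8 | m = 3.5 |
|---|---|---|---|
| 0.3 | 10% | 7% | 5% |
| 0.5 | 16% | 11% | 9% |
| 1.0 | 30% | 21% | 16% |

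**Step 2: only values above 3.8 in the denominator.** P(X2 < 2.8 | X1 > 3.8) is about 0.1% at s = 0.3, 1-2% at s = 0.5 and 7-14% at s = 1.0. If the abolition threshold were also 3.8, the range returns to about 6-30%. The size therefore depends on two definitions that the plan leaves open.

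**Step 3: cross-check with another model.** Take two standard normal readings with test-retest correlation r and prevalence p. At p = 50% the share crossing back is 0.5 − arcsin(r)/π. For r = 0.90 this is 0.5 − 1.1198/3.1416 = 14.4%. For r = 0.70, 0.80 and 0.95 it is 25.3%, 20.5% and 10.1%. Over p = 30-70% and r = 0.70-0.95 the range is 6.3% (p = 70%, r = 0.95) to 36.5% (p = 30%, r = 0.70).

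**Step 4: position.** Section III does not say whether the seated or the reclined reading qualifies a participant. If either can, and the later reading is supine, then at p = 50% with an assumed cross-position correlation of 0.9r the share is 31.9%, 27.8%, 22.7% and 19.2% for r = 0.70, 0.80, 0.90 and 0.95.

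**Step 5: what the interval covers.** Suppose 50 participants are titrated and 40 are counted as abolished: 80%, exact 95% CI 66.3% to 90.0%. At p = 50% and r = 0.90, about 50 × 0.144 = 7 would cross back with no effect. If those 7 were below threshold at minimum EPAP, 40 − 7 = 33 of 50, or 66%, would have fallen only after EPAP rose. The planned interval reflects sampling error around 80% and says nothing about this split.

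**The case against.** Several points on the other side stand.

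- **A reference of sorts exists.** Screening ends with a fixed-pressure reading, supine or semi-recumbent, shortly before titration in a similar position. A reader might infer that the plan has no reference condition at all. That goes too far: the limitation is that this reading may also be the one that selected the participant.
- **EPAP 4 is not the screening condition.** Therapy adds pressure support of 6 cmH2O. A reader might infer that anyone below threshold at minimum EPAP is mere drift counted as a treatment success. The documents do not support that. Section IX speaks of abolition with Vector therapy, bi-level support is part of that therapy, and the plan sets no success criterion.
- **Some links are inferred.** The documents give a minimum EPAP but do not say that every titration starts there. They give no number for the abolition threshold and no rule for recording these cases. Final EPAP may be assessed by sponsor staff using software.
- **The model is simple.** Screening is a 5-minute test with validity checks, and titration is about 20 minutes of breath-by-breath control. If EFL reappeared, EPAP would be raised and the participant would leave the never-raised group. One independent second reading does not reproduce that.
- **The endpoint is modest.** "This will be a cross-sectional, non-randomized epidemiology study designed to assess the prevalence and severity of expiratory flow limitation" is how Section III describes the study, and abolition is a descriptive secondary percentage.

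These points limit the size and wording of the concern. They do not answer it, because one percentage still cannot show how much of the abolition followed a rise in EPAP.

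**Conclusion.** The concern holds in a limited form. Selection at 2.8 or above, an EPAP floor at the top of the screening range and a single unsplit percentage together mean that the reported figure can overstate what EPAP titration achieved. Participants may be below threshold at minimum EPAP through within-person variation, through pressure support, or both, and the plan as written cannot tell these apart from abolition after EPAP rose.

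The size cannot be fixed from the documents. At unchanged pressure and an assumed SD of 0.3-1.0 it is about 5-30% of those screened at 2.8 or above, and about 0.1-14% if only values above 3.8 count. These figures measure threshold crossing on a repeat reading; they do not predict this trial's result. The primary prevalence estimate is not affected by this point.

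**What to change.** 1. Reconcile Sections II and IX first: which device defines the denominator, whether indeterminate EFL is included, and whether abolition is judged during screening or titration. State the abolition threshold that the analysis uses.
2. In Section IX, report three groups, each with a binomial CI, from the Delta Xrs and EPAP values that Section VI already lists as recorded at screening and titration:
   - (a) below threshold with EPAP never raised above the minimum, labelled as below threshold at minimum EPAP and not as drift;
   - (b) below threshold only after EPAP rose above the minimum;
   - (c) not abolished.
3. Describe only (b) as abolition following EPAP titration. Without a control period, even (b) shows sequence and does not prove cause.
4. Keep the full-sample Final EPAP correlations as the main analysis. A version without group (a) can be supplementary only: it selects on Final EPAP, removes its lowest values and restricts its range, and the report should say so.

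The cost is wording in Sections II and IX and a three-row table. No new measurement, visit or device setting is needed. The downside for the sponsor is that the percentage attributed to titration will be lower whenever group (a) is not empty.
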